3.2 Exclusion Criteria

- 3.2.1 Known hypersensitivity to thalidomide or lenalidomide (if applicable).
- 3.2.2 The development of erythema nodosum if characterized by a desquamating rash while taking thalidomide or similar drugs.
- 3.2.3 Known seropositive for human immunodeficiency virus (HIV). HIV testing is not required. Hepatitis testing is not required.
- 3.2.4 Patients who have had a myocardial infarction within 6 months of enrollment or has New York Heart Association (NYHA) Class III or IV heart failure, uncontrolled angina, uncontrolled ventricular arrhythmias, or electrocardiographic evidence of acute ischemia or active conduction system abnormalities.
- 3.2.5 Any serious medical condition laboratory abnormality or psychiatric illness that would prevent the subject from signing the consent form.
- 3.2.6 Any condition, including laboratory abnormalities, that in the opinion of the investigator places the subject at unacceptable risk if he/she were to participate in the study or confounds the ability to interpret data from the study.
- 3.2.7 Patients with major surgery within 28 days prior to treatment.
- 3.2.8 Patients with any serious medical or psychiatric illness that could, in the investigator's opinion, potentially interfere with the completion of treatment according to this protocol.
- 3.2.9 Patient has received an investigational agent or cytotoxic chemotherapy (excluding hydroxyurea) within 7 days of study entry. If an LP is performed for clinical care, intrathecal chemotherapy (although not systemic chemotherapy) may be given as prophylaxis per institutional standard of care, but should be completed >24 hours prior to administration of protocol therapy.
- 3.2.10 Patients with acute promyelocytic leukemia.
- 3.2.11 Females who are pregnant

3.3 Inclusion of Women and Minorities

Both men and women of all races and ethnic groups are eligible for this trial. Women and minorities are included in the eligibility criteria. We do not anticipate that women or minorities will have increased toxicity with this treatment approach. Gender, race and ethnicity will be recorded in our database, per standard procedures.

3.4 Consent

Patients who are referred to the participating institutions for consideration of treatment of acute myelogenous leukemia will be considered for participation. Patients with AML who have relapsed or refractory disease are eligible for this study. Treatment recommendations are discussed thoroughly with patient and family. The alternative forms of therapy, as far as they exist, are presented as objectively as possible. The risks and hazards of the procedure are explained to the patient and family. It will be pointed out specifically that some aspects of this treatment are considered experimental. Consent is obtained using forms approved by participating site's Institutional Review Board.

4. REGISTRATION PROCEDURES

4.1 General Guidelines for DF/HCC Institutions

Institutions will register eligible participants in the Clinical Trials Management System (CTMS) OnCore. Registrations must occur prior to the initiation of protocol therapy. Any participant not registered to the protocol before protocol therapy begins will be considered ineligible and registration will be denied.

An investigator will confirm eligibility criteria and a member of the study team will complete the protocol-specific eligibility checklist.

Following registration, participants may begin protocol therapy. Issues that would cause treatment delays should be discussed with the Overall Principal Investigator (PI). If a participant does not receive protocol therapy following registration, the participant's registration on the study must be canceled. Registration cancellations must be made in OnCore as soon as possible.

4.2 Registration Process for DF/HCC Institutions

DF/HCC Standard Operating Procedure for Human Subject Research Titled *Subject Protocol Registration* (SOP #: REGIST-101) must be followed.

4.3 General Guidelines for Other Investigative Sites

Eligible participants will be entered on study centrally at Massachusetts General Hospital by the Coordinating Center. All sites should contact the Coordinating Center to verify treatment availability.

Following registration, participants may begin protocol treatment. Issues that would cause treatment delays should be discussed with the Principal Investigator/Sponsor. If a participant does not receive protocol therapy following registration, the participant's registration on the study must be canceled. The Coordinating Center should be notified of cancellations as soon as possible.

4.4 Registration Process for Other Investigative Sites

To register a subject, the following documents should be completed by the participating institution and forwarded to the Coordinating Center:

- Copy of source documentation for inclusion/exclusion criteria and screening procedures, including but not limited to
 - Pathology report
 - Medical history and physical exam
 - Laboratory reports
 - Radiology results/reports
 - Echo or MUGA report
 - Concomitant medication list

CONFIDENTIAL

This document is confidential. Do not disclose or use except as authorized.

- Demographics information
- Signed study consent form
- Study Entry Note
- HIPAA authorization form, if applicable
- Eligibility checklist

The Coordinating Center will review the above documentation to verify eligibility and consent. To complete the registration process, the Coordinating Center will follow DF/HCC Standard Operating Procedure for Human Subject Research Titled *Subject Protocol Registration* (SOP #: REGIST-101) and register the participant on the protocol. Once registered, a confirmation email with the participant study number, and if applicable the dose treatment level, will be sent to the participating site.

NOTE: Registrations can only be conducted by the Coordinating Center during the business hours of 8:30 AM and 5:00 PM Eastern Standard Time (or Eastern Daylight Time when applicable), Monday through Friday. A complete registration packet, including all documents listed above, must be received at least 24 hours *prior to* the anticipated registration to ensure adequate review. Same day treatment registrations will only be accepted with prior notice and discussion with the DF/HCC Lead Institution.

Treatment may not begin without confirmation from the Coordinating Center that the participant has been registered.

5. TREATMENT PLAN

5.1 Treatment Regimen

	Day 1	Day 2	Day 3	Day 4	Day 5	Day 6	Day 7	Day 8	Day 9	Day 10
Mitoxantrone (intravenous)				X	X	X	X	X		
Etoposide (intravenous)				X	X	X	X	X		
Cytarabine (intravenous)				X	X	X	X	X		
Lenalidomide (oral)	X	X	X	X	X	X	X	X	X	X

Patients will receive all treatment on an inpatient basis. All chemotherapy doses will be based on actual weight obtained on Day 1 of the treatment cycle. The total administered doses of the MEC chemotherapy will be calculated using actual weight and may be rounded up or down within a range of 5% of the actual calculated dose. Any dose modifications in the mitoxantrone, etoposide, and cytarabine chemotherapy are per physician discretion or institutional practice (please refer to section 6.3, table 5), with approval from the overall PI.

CONFIDENTIAL

This document is confidential. Do not disclose or use except as authorized.

Administer chemotherapeutic agents according to institutional policies and procedures. Mitoxantrone will be administered first, followed by etoposide, followed by cytarabine. Patients will receive only one cycle of treatment as outlined in tables 1 and 2. There is no retreatment as a part of this protocol. See section 6 (Dosing delays/Dose modifications) for further information on dose modifications and interruptions. Premedications will be given per institutional standards.

Table 2: Dosing information

Agent	Dose	Route	Schedule
Mitoxantrone	8 mg/m ² /day	IV infusion over approx 6-10 minutes daily or per institutional standards for 5 days	Days 4 – 8
Etoposide	100 mg/m ² /day	IV over approx 1 hour daily or per institutional standards for 5 days	Days 4 – 8
Cytarabine	1000 mg/m ² /day	IV over approx 1 hour daily or per institutional standards for 5 days	Days 4 – 8
Lenalidomide	50 mg	Orally	Days 1– 10

Following reinduction therapy, patients may be treated further according to their treating physician. Patients who achieve a CR or CRi, as well as those who are otherwise deemed eligible, are recommended to proceed with allogeneic hematopoietic stem cell transplantation if possible. Otherwise patients are recommended to have further consolidation according to their treating physicians.

5.2 Pre-Treatment Criteria

Patients must meet eligibility in order to be enrolled on the study. Eligibility criteria does not need to be reconfirmed on Day 1 of treatment. There are no additional pretreatment criteria on Day 4 of treatment.

5.3 Agent Administration

Treatment will be administered on an inpatient basis. Expected toxicities and potential risks for mitoxantrone, etoposide, cytarabine, and lenalidomide are outlined in Toxicities and Dosing Delays/Dose Modification (section 6).

Administer chemotherapeutic agents according to institutional policies and procedures. Lenalidomide should be administered prior to MEC each day. During the administration of MEC, mitoxantrone will be administered first, followed by etoposide, followed by cytarabine.

General dosing guidelines for lenalidomide are provided below. Please refer to the dosage and

CONFIDENTIAL

This document is confidential. Do not disclose or use except as authorized.

administration schedule specified in the prescribing information.

5.3.1 Lenalidomide Dosing Guidelines

Lenalidomide should be taken orally at about the same time each day. The capsules should not be opened, broken, or chewed. Lenalidomide capsules should be swallowed whole, preferably with water, either with or without food. If a dose of lenalidomide is missed, it should be taken as soon as possible on the same day (until midnight). If it is missed for the entire day, it should not be made up. Vomited doses will not be made up. Do not take 2 doses at the same time.

5.3.1.1 Patients Receiving Concomitant Digoxin

Periodic monitoring of digoxin levels in patients receiving this medication concomitantly with lenalidomide is recommended in accordance with clinical judgment and based on standard clinical practice.

5.3.1.2 Patients Receiving Concomitant Warfarin

Monitoring of warfarin concentration in accordance with standard practice is advised during treatment with lenalidomide.

5.3.1.3 Elderly Patients

No dedicated clinical studies have been conducted to evaluate the PK of lenalidomide in the elderly. However, results of population PK analyses (subject ages ranging from 39 to 85 years old) suggest that age does not influence the disposition of lenalidomide. No lenalidomide dose adjustments are needed.

5.3.1.4 Patients with Impaired Renal Function

Lenalidomide is primarily excreted unchanged by the kidney; for other approved indications, starting dose adjustment is recommended in patients with CKD. Based on a PK study in subjects with CKD due to nonmalignant conditions, lenalidomide starting dose adjustments are recommended for patients with $\text{CrCl} < 60 \text{ mL/min}$; therefore, patients must have a $\text{CrCl} \geq 60 \text{ mL/min}$ to be eligible for this study.

Because lenalidomide is primarily excreted unchanged by the kidney, monitoring of renal function is advised. No dose adjustments are required for patients with $\text{CrCl} \geq 60 \text{ mL/min}$. Patients must have eGFR of $\geq 60 \text{ mL/min}$ and $\text{Cr} < 2 \text{ mg/dL}$ to enroll on the study. Refer to Section 6.2, Table 4 for lenalidomide dose adjustment recommendations if patients develop worsened renal function while on treatment.

5.3.1.5 Prohibited Medications

Any investigational agent or medication intended to treat the malignancy.

CONFIDENTIAL

This document is confidential. Do not disclose or use except as authorized.

5.4 General Concomitant Medication and Supportive Care Guidelines

5.4.1 Encouraged Supportive Care and Allowed Concomitant Medications

Infection Prophylaxis may be per institutional guidelines. The following practices are suggested prophylactic antibiotics (such as Levaquin or other appropriate agent) against gram negative organisms while patient is neutropenic; antiviral therapy against herpes viruses with acyclovir or an appropriate substitution; and antifungal prophylaxis with fluconazole (or another appropriate agent). Patients should have excellent oral care per institutional standards. Patients with fever and neutropenia should be treated with broad spectrum antibiotics per institutional guidelines.

Recombinant Granulocyte Colony Stimulating Factor (G-CSF) may be administered intravenously or subcutaneously at the discretion of the investigator and per institutional guidelines. G-CSF is recommended for patients older than age 60 after the completion of chemotherapy and for all patients with serious infections.

Prophylaxis against tumor lysis syndrome is recommended and can be administered per institutional guidelines.

Transfusion support per Dana-Farber/Harvard Cancer Center guidelines will be provided, and patients may be managed per local standards.

Central venous access is suggested prior to the start of chemotherapy.

Antiemetics will be used per standard practices.

Hyperalimentation (TPN) will be provided at the treating physician's discretion.

Decadron eye drops are recommended and can be dosed per institutional guidelines. Suggested dosing is as follows:

- Two drops of dexamethasone suspension 0.1% to both eyes every 6 hours starting with first dose of cytarabine on day 4 and continued for 72 hours after the last dose of cytarabine on day 8.

Neurologic assessments for cerebellar function are recommended while patient is receiving cytarabine.

After hospitalization, subjects will be followed closely to monitor for complications related to chemotherapy. Patients will receive standard post-chemotherapy discharge teaching and guidelines to prevent infection.

Prophylactic anticoagulation is not recommended considering the low platelet count after induction chemotherapy.

5.4.2 Anticoagulation consideration

CONFIDENTIAL

This document is confidential. Do not disclose or use except as authorized.

Lenalidomide increases the risk of thrombotic events in patients who are at high risk or with a history of thrombosis, in particular when combined with other drugs known to cause thrombosis. Due to the thrombocytopenia with this chemotherapy regimen, anticoagulation and antiplatelet agents are not recommended.

When lenalidomide is combined with other agents such as steroids (e.g. dexamethasone, prednisone), anthracyclines (Doxil, Adriamycin) and erythropoietin, the risk of thrombosis is increased.

5.5 Criteria for Taking a Participant Off Protocol Therapy

Duration of therapy will depend on individual response, evidence of disease progression and tolerance. In the absence of treatment delays due to adverse event(s), treatment may continue until one of the following criteria applies:

- Disease progression
- Intercurrent illness that prevents further administration of treatment
- Unacceptable adverse event(s) or those listed in table 3 as requiring treatment discontinuation
- Participant demonstrates an inability or unwillingness to comply with the oral medication regimen and/or documentation requirements
- Participant decides to withdraw from the protocol therapy
- General or specific changes in the participant's condition render the participant unacceptable for further treatment in the judgment of the treating investigator
- The subject needs a medication that is not part of this study (e.g additional chemotherapy for relapsed or progressive disease)
- The investigator feels this study protocol would not be in the subject's best interest
- Patient completed all treatment as outlined in the protocol

Participants will be removed from the protocol therapy when any of these criteria apply. Alternative care options will be discussed with the participant.

The reason for removal from protocol therapy, and the date the participant was removed, must be documented in the case report form (CRF). The DF/HCC research team will update the relevant Off Treatment/Off Study information in OnCore. The Coordinating Center will update this information for external site participants.

In the event of unusual or life-threatening complications, treating investigators must immediately notify the Overall PI, [name] at [REDACTED].

5.6 Duration of Follow Up

Participants will be followed for at least 50 days after the start of protocol treatment. Participants will be followed for relapse and survival at 3 months after treatment, and then every

CONFIDENTIAL

This document is confidential. Do not disclose or use except as authorized.

six months until 3 years from start of treatment, including those patients who are removed from the study treatment prior to completing the 50 day toxicity period.

Participants removed from protocol therapy for unacceptable adverse event(s) will be followed until resolution or stabilization of the adverse event.

5.7 Criteria for Taking a Participant Off Study

Study subjects may withdraw their consent to participate in this trial at any time. Once withdrawn, the study subject will receive usual care considered standard and routine for their individual case.

Participants will be removed from study when any of the following criteria apply:

- Lost to follow-up
- Withdrawal of consent for data submission
- Death
- Completed all follow-up per protocol

The reason for taking a participant off study, and the date the participant was removed, must be documented in the case report form (CRF). The DF/HCC research team will update the relevant Off Treatment/Off Study information in OnCore. The Coordinating Center will update this information for external site participants.

6. DOSING DELAYS/DOSE MODIFICATIONS

Any dose modifications or delays in the reinduction chemotherapy regimen of mitoxantrone, etoposide, and cytarabine should be per the treating physician and institutional practice, with approval from the overall PI (also please refer to section 6.3, table 5).

There may be two dose reductions in lenalidomide per patient. Reduction of lenalidomide dose may be modified as follows:

Table 3: Lenalidomide Dose Reductions	
Dose Level	Lenalidomide dose
1 (starting dose)	50 mg
-1	25mg
-2	10 mg

No Lenalidomide will be given after Day 10, even if there are missed doses.

Dose delays and modifications will be made as indicated in Table 4. The descriptions and grading scales found in the revised NCI Common Terminology Criteria for Adverse Events (CTCAE) version 4.03 will be utilized for dose delays and dose modifications. A copy of the CTCAE version 4.03 can be downloaded from the CTEP website http://ctep.cancer.gov/protocolDevelopment/electronic_applications/ctc.htm.

CONFIDENTIAL

This document is confidential. Do not disclose or use except as authorized.

6.1 Toxicity Management

Significant toxicity is expected in this leukemia reinduction protocol. Patients will receive supportive care and medical management of toxicity.

Antiemetics are recommended for management of nausea and vomiting.

Stool cultures for C. Diff are recommended for patients with diarrhea. If negative, antidiarrheals should be used as clinically indicated

For management of neutropenia/fever myeloid growth factors can be considered. Platelet transfusions should be considered for management of patients with a platelet count of <10K or bleeding.

Local steroid creams are recommended as clinically indicated for the management of rashes.

6.2 Dose Modifications for Lenalidomide

Table 4: Dose modifications for Lenalidomide				
Toxicity	Grade 1	Grade 2	Grade 3	Grade 4
Nausea	no change in dose	no change in dose	no change in dose	no change in dose
Vomiting	no change in dose	no change in dose	no change in dose	no change in dose
Diarrhea	no change in dose	no change in dose	no change in dose	no change in dose
Neutropenia	no change in dose	no change in dose	no change in dose	Continue lenalidomide dose. Follow CBC. Consider G-CSF.
Thrombocytopenia	no change in dose	no change in dose	Continue lenalidomide dose. Follow CBC. Consider platelet transfusion	Continue lenalidomide dose. Follow CBC. Consider platelet transfusion
Neutropenia associated with fever (temperature \geq 38.5° C)	N/A	N/A	Continue lenalidomide dose. Follow CBC. Consider G-CSF.	Continue lenalidomide dose. Follow CBC. Consider G-CSF.

CONFIDENTIAL

This document is confidential. Do not disclose or use except as authorized.

Table 4: Dose modifications for Lenalidomide

Toxicity	Grade 1	Grade 2	Grade 3	Grade 4
Non-blistering rash thought related to Lenalidomide	no change in dose	no change in dose	Hold lenalidomide. If resolves to \leq grade 1 restart lenalidomide at next lower dose level and continue through the remainder of the scheduled treatment. Omitted doses are not made up.	Discontinue lenalidomide. Remove patient from study.
Desquamating (blistering) rash thought related to lenalidomide	Discontinue lenalidomide. Remove patient from study	Discontinue lenalidomide. Remove patient from study	Discontinue lenalidomide. Remove patient from study	Discontinue lenalidomide. Remove patient from study
Neuropathy	no change in dose	no change in dose	Hold (interrupt) lenalidomide. If resolves to \leq grade 1, restart lenalidomide at next lower dose level and continue through the remainder of the scheduled treatment. Omitted doses are not made up.	Discontinue lenalidomide. Remove patient from study.
Venous thrombosis or embolism	No change in dose	No change in dose	Hold (interrupt) lenalidomide and start therapeutic anticoagulation, if appropriate. Restart lenalidomide at investigator's discretion (maintain dose level).	Hold (interrupt) lenalidomide and start therapeutic anticoagulation, if appropriate. Restart lenalidomide at investigator's discretion (maintain dose level).

CONFIDENTIAL

This document is confidential. Do not disclose or use except as authorized.

Table 4: Dose modifications for Lenalidomide

Toxicity	Grade 1	Grade 2	Grade 3	Grade 4
Acute kidney injury	No change in dose	Decrease lenalidomide dose by one level according to Table 3.	Hold lenalidomide. If resolves to \leq grade 2, restart lenalidomide at next lower dose level and continue through the remainder of the scheduled treatment. Omitted doses are not made up.	Hold lenalidomide. If resolves to \leq grade 2, restart lenalidomide at next lower dose level and continue through the remainder of the scheduled treatment. Omitted doses are not made up.
Other clinically significant, non-hematologic toxicity thought to be related to lenalidomide	No change in dose	No change in dose	Hold lenalidomide. If resolves to \leq grade 2, restart lenalidomide at next lower dose level and continue through the remainder of the scheduled treatment. Omitted doses are not made up.	Hold lenalidomide. If resolves to \leq grade 2, restart lenalidomide at next lower dose level and continue through the remainder of the scheduled treatment. Omitted doses are not made up.

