Simon's two stage optimal design is used to compute the sample size. A total number of 40 patients is needed in order to detect a 20% CR rate increase assuming the CR for null hypothesis is 25% with a 90% power and 9% type I error. The study will be reevaluated if 4 or fewer responses out of 18 patients are observed and the study will be declared inactive if fewer than 14 responses are seen in the total 40 patients. The probability of stopping at the first stage is 0.52.

Accrual Objective: 40 - 42 patients in order to enroll 40 evaluable patients.

Accrual Period: The estimated accrual period is 2.5 years

Eligibility Criteria:

The following criteria must be met prior to enrolling.

- Acute myelogenous leukemia diagnosed by WHO criteria with one of the following:
 - Primary refractory disease following ≥ 1 cycle of induction chemotherapy.

CONFIDENTIAL

This document is confidential. Do not disclose or use except as authorized.

- First relapse or higher. Patients with primary or secondary acute myelogenous leukemia are eligible. Patients with biphenotypic leukemia are eligible.
- 18-70 years
- LVEF \geq 50%
- ECOG Performance status 0-2
- Creatinine < 2.0 mg/dl and eGFR ≥ 60 mL/min.
- Total bilirubin $< 1.5 \times$ institutional ULN
- AST (SGOT) and ALT (SGPT) $\leq 3 \times$ institutional ULN
- Able to adhere to study schedule and other protocol requirements
- Patients may receive hydroxyurea, steroids, or leukapheresis as necessary until Day 5 of treatment.

Treatment Description:

Patients will receive only one cycle of treatment, as below:

1. Lenalidomide Days 1-10
2. Mitoxantrone by IV infusion over approximately 6-10 minutes for 5 days (days 4-8)
3. Etoposide IV over approximately 1 hour daily for 5 days (days 4-8)
4. Cytarabine IV over approximately 1 hour daily for 5 days (days 4-8).

	Day 1	Day 2	Day 3	Day 4	Day 5	Day 6	Day 7	Day 8	Day 9	Day 10
Mitoxantrone (intravenous)				X	X	X	X	X		
Etoposide (intravenous)				X	X	X	X	X		
Cytarabine (intravenous)				X	X	X	X	X		
Lenalidomide (oral)	X	X	X	X	X	X	X	X	X	X

Study Duration:

Participants will be followed for at least 50 days after the start of protocol treatment.

Participants will be followed for relapse and survival at 3 months after treatment, and then every six months until 3 years from start of treatment. Patients removed from the study treatment will continue to be followed for relapse and survival for up to three years following initiation of study treatment

CONFIDENTIAL

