6.3 Dose Modifications for Mitoxantrone, Etoposide, Cytarabine

Table 5: Dose modifications for mitoxantrone, etoposide, cytarabine

Toxicity	Grade 1	Grade 2	Grade 3	Grade 4
Nausea	no change in dose			
Vomiting	no change in dose			
Diarrhea	no change in dose			
Neutropenia	no change in dose			
Thrombocytopenia	no change in dose			
Non-blistering	no change in	no change in	no change in dose	no change in dose

CONFIDENTIAL

This document is confidential. Do not disclose or use except as authorized.

rash	dose	dose		
Table 5: Dose modifications for mitoxantrone, etoposide, cytarabine				
Toxicity	Grade 1	Grade 2	Grade 3	Grade 4
Desquematting (blistering) rash	no change in dose	no change in dose	no change in dose	no change in dose
Neuropathy	no change in dose	no change in dose	no change in dose	no change in dose
Other clinically significant non-hematologic toxicity	no change in dose	no change in dose	Per physician discretion or institutional practice	Per physician discretion or institutional practice

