10.4 Long Term Follow Up

Participants will be followed for at least 50 days after the start of protocol treatment to assess for response to treatment and adverse events. At the completion of the study treatment, participants will be followed for relapse and overall survival outcomes for a total of 3 years from the start of treatment. These outcomes should be assessed at approximately 3 months after treatment, and then approximately every six months until the 3 year follow-up has been reached.

Patients removed from the study treatment early, for instance patients with refractory disease who go onto another therapy within 45 days of the study therapy, and will continue to be followed for relapse and survival for up to three years following initiation of study treatment.

Participants removed from protocol therapy for unacceptable adverse event(s) will be followed until resolution or stabilization of the adverse event. They will then also be followed at the above approximate intervals for relapse and survival outcomes.

Baseline evaluations are to be conducted within 21 days prior to the start of protocol therapy.

Assessments must be performed prior to administration of any study agent. Study assessments should be administered within \pm 3 days of the protocol-specified date, unless otherwise noted.

Table 6. Required Study Data.

	Pre-treatment (within 21 days)	Weekly (+/- 3 days)	Count recovery or Day +35 (+/- 3 days)	Day +38	Day +45 +/- 3 days
Medical History and Physical Exam	X				
CBC with diff	X	X (Diff optional)			X
Comprehensive chemistry with renal and liver functions ¹	X	X			X
ABO/Rh	X				X
Bone marrow biopsy and aspirate ²	X		X		X
Informed Consent	X				
History and physical	X	X			X
Performance Status	X				
EKG	X				
MUGA or ECHO	X				

CONFIDENTIAL

This document is confidential. Do not disclose or use except as authorized.

Chest x-ray	X				
Toxicity assessment ⁴	X	ongoing throughout			
Enroll in REMS	X				
Pregnancy Test Child Bearing Female	X			X	
Optional Research Studies	X ⁵	b	X		

¹ Chemistry testing to include creatinine, eGFR, BUN, potassium, sodium, chloride, HCO3, glucose, magnesium, phosphorus, calcium. Liver function testing to include ALT, AST, total bilirubin, alkaline phosphatase, albumin.

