13.1.1 Evaluation of toxicity

All participants will be evaluable for toxicity from the time of their first treatment up until day 50 or the initiation of other therapy. In the phase I study of 35 patients, 3 dose limiting toxicities were noted due to prolonged count recovery. In the current study, we will monitor for toxicities and assess them as a part of the two stage design described above. If, within the first 10 patients on study, 3 or more experience prolonged neutrophil or platelet recovery beyond day 45 in the absence of disease, or other unacceptable toxicities felt related to the study regimen, we will put the study on hold to investigate further enrollment. The probability of putting the study on hold is 7%, if the true probability of delayed count recovery is 10%.

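### Table 4 takes patients off study for certain toxicities, contrary to the off-study criteria in Section 5.7 and the follow-up required by Sections 5.6 and 10.4

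*Combined protocol and SAP*

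**What the plan says.** Section 6.2, Table 4 gives the lenalidomide action for each toxicity and grade. In three rows it instructs the site: "Discontinue lenalidomide. Remove patient from study". The rows are blistering rash thought related to lenalidomide (all four grades), non-blistering rash thought related to lenalidomide (grade 4) and neuropathy (grade 4). The neuropathy row carries no relatedness condition.

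Other sections deal with the same patients:

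- **Section 5.7** introduces its off-study list with "Participants will be removed from study when any of the following criteria apply". The four entries are loss to follow-up, withdrawal of consent for data submission, death, and completion of follow-up.
- **Section 5.5** makes unacceptable adverse events, and "those listed in table 3 as requiring treatment discontinuation", reasons for leaving protocol therapy.
- **Section 5.6**: "Participants removed from protocol therapy for unacceptable adverse event(s) will be followed until resolution or stabilization of the adverse event".
- **Section 10.4** repeats that rule and adds: "They will then also be followed at the above approximate intervals for relapse and survival outcomes".
- **Synopsis, Study Duration**: "Patients removed from the study treatment will continue to be followed for relapse and survival", for up to three years.
- **Section 13.1.1**: "All participants will be evaluable for toxicity from the time of their first treatment up until day 50 or the initiation of other therapy".
- **Section 6.3, Table 5** leaves the MEC dose unchanged for blistering rash, non-blistering rash and neuropathy at every grade.

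**The concern.** The protocol treats coming off therapy and coming off study as separate events with separate sections, and staff record each in the case report form. Table 4 uses the off-study term for a toxicity, which elsewhere in the protocol is only a reason to come off therapy.

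A dose-modification table is what a site consults when a toxicity occurs. A site that took this one at its word would end study participation in a patient who had just had one of these toxicities. Sections 5.6 and 10.4 require that same patient to be followed for the event, and then for relapse and survival to three years. No text reconciles the two instructions.

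**Working it through.** The plan gives no figure on this point, so the check is a count and a comparison of texts.

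**1. How much of Table 4 is affected.** The rows are nausea, vomiting, diarrhea, neutropenia, thrombocytopenia, neutropenia with fever, non-blistering rash, blistering rash, neuropathy, venous thrombosis or embolism, acute kidney injury, and other non-hematologic toxicity. That is 12 rows × 4 grades = 48 cells. The off-study instruction stands in 4 (blistering rash) + 1 (non-blistering rash) + 1 (neuropathy) = 6 cells, in 3 of the 12 rows.

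**2. Which texts conflict, and how directly.**

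| Place | Rule for a patient stopped for toxicity | Conflict with Table 4 |
|---|---|---|
| 5.7 | Toxicity is not an off-study reason | Direct |
| 5.6 | Follow the event until it settles; relapse and survival follow-up continues to 3 years | Direct |
| 10.4 | Same, with relapse and survival follow-up stated for these patients | Direct |
| Synopsis | Patients off study treatment stay in relapse and survival follow-up | By inference |
| 13.1.1 | Everyone evaluable for toxicity to day 50 or other therapy | By inference |
| 5.5 | Toxicity is a reason to leave therapy | By inference; it is not a follow-up rule |

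**3. One patient traced through.** Take a grade 1 blistering rash thought related to lenalidomide on Day 3. Lenalidomide began on Day 1 and MEC is due on Days 4 to 8 (Section 5.1).

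- Table 4 read literally: off study on Day 3.
- Sections 5.6 and 10.4: at least 50 days of follow-up, the rash followed until it settles, then contact at about 3 months and six-monthly to 3 years.
- Table 5: full-dose MEC from Day 4.
- Section 5.5: a patient who meets a listed criterion leaves the protocol therapy, which on its face is the whole regimen.

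So the texts disagree on follow-up and also leave it unclear whether MEC goes ahead.

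**4. What other sections would preserve under the literal reading.**

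- Section 7.2.4 requires serious events unresolved when participation ends to be followed to an outcome. Section 7.2.1 describes grade 4 as life-threatening, and Section 7.2.2 lists life-threatening events as serious. This should cover the three grade 4 cells (both rashes and neuropathy), as far as the event itself goes.
- Section 7 allows, but does not require, contact with patients who have continuing toxicity at the off-study visit.
- Section 7 also sets adverse event recording to 28 days after the last dose. After a full course that is Day 10 + 28 = Day 38. If the patient in step 3 receives nothing after Day 3, it is Day 3 + 28 = Day 31. Neither reaches Day 45 or Day 50.

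**5. What is left uncovered.** Three cells remain (blistering rash, grades 1 to 3), where a non-serious event has no mandatory follow-up to resolution. In all six cells, toxicity assessment to Day 45 or 50 and relapse and survival follow-up would be lost. The Section 13.1.1 hold counts count recovery delayed beyond Day 45 in the first 10 patients, and that cannot be seen in someone taken off study earlier. The same hold also counts other unacceptable related toxicities, so such a patient might already count for that reason.

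**6. The cross-reference.** Section 5.5 points to Table 3 for toxicities that require discontinuation. Table 3 (Section 6) lists only the dose levels of 50, 25 and 10 mg; the discontinuation entries are in Table 4.

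**The case against.** The strongest reply is that the intended meaning is plain. Section 5.5 describes these table entries as requiring treatment discontinuation and places them under off-therapy criteria. Sections 5.6 and 10.4 then say what follows. On that view Table 4 uses study loosely for study treatment, and a trained site would not be misled. This is probably what was meant, and it keeps the point minor. It does not make the wording right. The instruction is operative text, and even the milder reading leaves open whether MEC is given.

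It is also fair that Section 7.2.4 already protects follow-up of serious events, and that the Table 3 reference is a numbering slip, since Section 6 sends readers to Table 4 for modifications. Both stand. A reader might infer that all event follow-up is lost, or that six sections flatly contradict Table 4. The documents support neither: serious events stay covered, and only Sections 5.7, 5.6 and 10.4 conflict directly. Section 5.7 also does not say that its list is exclusive, although nothing adds toxicity to it.

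A reader might further infer informative censoring of overall or relapse-free survival, or bias in the response rate. That is not supported. The closing paragraph of Section 13 excludes from the analyses, and replaces, patients who do not complete the 10 days of therapy. Patients whose lenalidomide stops early may therefore be out of those estimates whatever Table 4 says. That exclusion concerns the analysis set; it takes no one off study and does not resolve the conflict.

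**Conclusion.** The point holds and is minor: the instruction is wrong as written in six of 48 cells. It conflicts directly with Sections 5.7, 5.6 and 10.4, and fits poorly with the synopsis and with day-50 toxicity evaluability in Section 13.1.1. Taken literally, it would cost mandatory follow-up of non-serious blistering rash, toxicity assessment to Day 45 or 50, and relapse and survival follow-up.

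The documents give no frequency for these toxicities, so the number of patients is unknown; that it is small is an assumption. No effect is claimed on the primary endpoint, on the two-stage design, or on the mortality, relapse or survival estimates. The conclusion assumes that a site might follow the table as worded, and that grade 4 events would be classed as serious.

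One might also read Table 5 as settling that MEC continues. It does not, because Section 5.5 points the other way. That is a clinical decision for the sponsor.

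**What to change.** 1. In the six Table 4 cells, replace the off-study instruction with wording that stops lenalidomide and keeps the patient on study, for example: *Discontinue lenalidomide; patient remains on study for follow-up per 5.6 and 10.4.*
2. Have the sponsor state whether MEC continues after these events, as Table 5 implies, or all protocol therapy stops, as Section 5.5 implies. Then align Section 5.5 and Table 5 with that decision.
3. In Section 5.5, change the reference from Table 3 to Table 4. This is clerical.

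Items 1 and 3 change six table cells and one cross-reference. They leave the design, sample size and analysis untouched. Item 2 needs a clinical decision and could change treatment for a patient with one of these events; beyond that it is a wording change in Section 5.5 or Table 5.
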